- Mean duration of use of β 2-agonist was used during each cold/asthma flare-up reported verbally or documented on the validated written 'Asthma Flare-up Diary for Young Children' over the time frame of 7 months (with each means of recording considered as a separate outcome).
- Mean of out-of-pocket asthma related expenses per exacerbation
- The sum of the daily ADYC scores as a measure of the severity of asthma symptoms during exacerbations, completed daily by parents using the validated 17-item, each scored from 1 (best) to 7 (worst), Asthma Flare-Up Diary for Young Children symptoms (ADYC) and standardized over 7 days
- Mean intensity of β 2-agonist use reported on the diary as
 - Cumulative rescue bronchodilator use: \sum daily number of puffs from the first day until last day of use until last day of use, inclusively. Units [puffs/episode]
 - Average rescue bronchodilator score = Cumulative rescue bronchodilator use \div duration of use, units [average puffs/day]
- Mean parents' functional status during exacerbations per child
 - Reported as the mean ECAP score
 - Reported as Global functional status on a 7-point likert scale from 1-not at all, to 7-extremely

Primary Efficacy Analyses

A Poisson regression model, will be estimated, using an ITT approach, including only randomization group as a predictor and adjusting only for the stratification of randomization by clinical site. This model will be used to estimate the incidence rate ratio comparing the mean number of oral corticosteroids (OCS) per child during the 7-month follow-up by study group. If overdispersion is present, a negative binomial model will be used. If there are large variations in person-time an adjustment using an offset term will be made. Two sensitivity analysis are planned; 1) the incidence rate ratio will be stratified by the month of recruitment to explore the possibility of effect modification by seasonality and 2) the incidence rate ratio will be stratified by year of the pandemic (2000-2001) to assess the possibility of effect modification by exposure to the COVID-19 pandemic period. The original analysis plan included a fixed effect for each site. However, for sites with a very small number of recruited patients, these small sites may be grouped together.

Secondary outcome analyses

Secondary outcomes will be analyzed using the same modeling strategy as the primary efficacy analysis. For outcomes collected as count variables (e.g. number of laboratory-confirmed viral upper respiratory tract infections (URTIs), days with asthma symptoms, days of rescue B agonist use, number of lost parental workdays) we will again use a Poisson or negative binomial model for differences by intervention group and adjusted only for study site.

For continuous outcomes including: severity of symptoms, duration of asthma symptoms per exacerbation, duration and intensity of rescue β_2 -agonists use per exacerbation, and functional status we will compare outcomes by treatment group using a generalized linear regression model approach. For outcomes with repeated measures, a GEE method will be used adjusting for the clustering of events in individual children and if indicated an offset variable for variations in person-time if relevant.

For binary outcomes, including treatment intensification, a generalized linear model with a log-linear link function will be used, again including a GEE method to adjust for repeated measures. All confidence intervals will be constructed using robust standard errors. No adjustment for multiple outcomes is planned.

Safety Outcomes:

The Mantel-Haenszel method, stratified by clinical site, will be used to compare dichotomous outcomes including:

- The proportion of children with at least one clinically significant occurrence of hypercalciuria and hypercalcemia,
- The proportion of children with one or more occurrences of elevated serum 25OHD (>250 nmol/L)
- Proportion of children experiencing an adverse event
- Proportion of children experiencing a serious adverse event

Documented adverse and serious adverse events will be summarized according to type using MEDRA classifications.

Significance thresholds:

A two-tailed alpha of 5% will be used for all statistical tests, ensuring that the results are assessed for significance on both ends of the distribution. One interim analysis was planned once 50% of patients have been recruited and their primary endpoint assessed. The O'Brien-Fleming stopping rules were meant be applied, with p-values for the two looks (one interim and one final) set at 0.003051 and 0.046946, respectively. As nearly all the nominal alpha is preserved for the final look, no adjustment to sample size is needed.

Subgroup Analyses

Potential modification of the effect of study intervention with vitamin D on primary and secondary outcomes will be assessed using the addition of interaction terms to the regression models. If there is a significant effect of the intervention, we will consider there as evidence of potential effect modification if inclusion of the interaction improves the overall model fit (using AIC/BIC criteria or R squared metrics), and if the interaction term is significant at an alpha of 0.20 or lower.

Statistical software and versions

The statistical analyses will be conducted using R 4.3.1 on Rstudio Server 2023.03.0. The following R packages are likely to be used based on the analysis requirements: base, stats, MASS, glm2, car, dplyr, tidyr, ggplot2, mice, Amelia, boot, heemod, BCEA.

Ancillary studies:

The economic evaluation will use standard trial-based economic evaluation methods. The intention is to provide the expected value of the intervention cost versus health care and family cost of exacerbations, effectiveness, and cost-effectiveness ratio with uncertainty around such values in terms of credible intervals.

References:

[name] FM, Jensen ME, Mendelson MJ, Parkin PC, Desplats E, Zhang X, Platt R. Asthma Flare-up Diary for Young Children to monitor the severity of exacerbations. *J Allergy Clin Immunol.* 2016 Mar;137(3):744-9.e6. doi: 10.1016/j.jaci.2015.07.028. Epub 2015 Sep 2. PMID: 26341275.

GINA 2024:www.ginasthma.com with ICS Doses based on Canadian Thoracic Society 2021 Guideline

Yang CL, et al. 2021 Canadian Thoracic Society Guidelines. *Can J Resp Crit Care Sleep Med.* 2021:1-41

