Total duration of β 2-agonist use.....	40
Number of lost parental workdays and productivity	41
Family expenses.....	42
Health care cost.....	42
Severity of asthma symptoms.....	42
Intensity of use of rescue B2-agonists.....	44

Parental functional status.....	45
Appendix 3: Coding for subgroup variables	45
Subgroup variables.....	45
Subgroups (pre-specified).....	45
Clinical Asthma Phenotype	46
Sex.....	47
Atopy.....	47
Body Mass Index (BMI) at baseline	47
Skin Color	48
Subgroups to consider (ad hoc)	48
Type 2 inflammation	48
Past Morbidity in previous 12 months	48
Prescribed GINA 4 Step-therapy at index visit.....	49

List of abbreviations

AE	Adverse event
AUC	area under the curve
CHUSJ	Centre Hospitalier Universitaire de Saint-Justine
CI	Confidence interval
CRF	Case report form
ED	Emergency department
kg	Kilogram
MD	Medical doctor
MedDRA	Medical dictionary for regulatory activities
mg	Milligram
Min	Minimum
OR	Odds ratio
SAE	Serious adverse event
SAP	Statistical analysis plan
SD	standard deviation

Introduction

Background: Preschoolers have the highest rate of acute care visits and hospitalisations of all age groups. Most exacerbations are triggered by upper respiratory tract infections (URTI), mainly in the fall/winter. New evidence suggests significant long-term sequelae of preschool asthma: irreversible lung obstruction by 6 years and chronic obstructive lung disease in adulthood. Risk factors of sequelae include frequency and severity of exacerbations, specific viral URTIs, and atopy. Prevention is the best approach to reduce morbidity. Vitamin D insufficiency is highly prevalent in Canadian preschoolers with recurrent asthma exacerbations (75%), increases further in winter, and is associated with more URTI and OCS use, indicative of moderate/severe exacerbations. A systematic 2016 review of randomised controlled trials (RCT) concluded that vitamin D supplements significantly decreased asthma exacerbations requiring rescue OCS (rate ratio: 0.63, high-quality evidence) with insufficient data to firmly conclude that findings apply to preschoolers with moderate/severe exacerbations.

Specific Objectives: To determine if vitamin D3 supplementation will reduce by 25% the number of exacerbations requiring rescue OCS per child (primary outcome), URTIs, and other markers of exacerbation frequency and severity, compared to placebo in preschoolers with moderate/severe exacerbations.

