The **ITT sample** includes all participants who are randomized into the study, regardless of whether they adhere to the study protocol or complete the study. The **per protocol sample** includes participants who adhered strictly to the study protocol without major deviations. This means they received the correct Study drug, swallowed more than 50% of Study Bolus, missed daily supplement intake for fewer than 40 days (or less than 20% of expected intake), did not experience unblinding of the study treatment and were eligible at randomization. For patients with a low daily Ca intake (< 350mg if aged 1-3 years; < 500 mg if aged 4-6 years), the bolus was administered only after receiving normal results for Ca, Ph, and ALP analyses. Additionally, there were no deviations impacting patient safety, rights, welfare, or data integrity.

The **complete case sample** includes all participants who completed the 7-month study period and provided the necessary data for primary and secondary endpoints. This includes participants who may have experienced major protocol deviations, such as incorrect study drug administration or missed daily supplements for up to 40 days, as well as minor deviations, such as delayed urine sample collections, as long as they did not withdraw from the study and their data is available for analysis.

Seven **subgroup analyses** were pre-specified at the start of the study as being of interest because of the potential for the relationship between vitamin D and asthma related outcomes to be modified by these characteristics. These include; Serum 25OHD Levels, ICS Therapy (Pre-emptive vs. Daily), Clinical Asthma Phenotype, Sex, Atopy, BMI category at baseline, Skin color according to the 6 category Fitzpatrick scale. An additional three variables were identified before analysis by group or unblinding, for exploration of subgroup effects. These include: Type 2 inflammation, OCS in the past 12 months, and step therapy using the GINA 2024 definitions.

Exposure(s), Endpoint(s) and Covariates

Exposure(s) of interest

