The exposure of interest is the administration of vitamin D3 as defined in the protocol intervention. Specifically, this involves receiving two 2mL oral boluses of 50,000 IU/mL (total dose of 100,000 IU) vitamin D3 (cholecalciferol) during 2 clinic visits (randomisation and 3.5 ± 0.5 months later), along with a daily dose of 400 IU vitamin D3. The control group receives 2 identical placebo boluses and a daily placebo dose. The intervention is designed to ensure a rapid and sustained increase in serum vitamin D levels, providing maximal group separation. Hence, the exposure variable will be binary, indicating whether a participant is in the intervention group or the control group.

The research nurses (or auxiliary nurses) were responsible for administering the oral bolus doses and providing the daily doses to participants. They ensured adherence to the bolus dose by administering it in the clinic. The bolus doses were prepared in 2 mL coded syringes, and the daily doses were provided in coded bottles, all dispensed in masked kits to maintain blinding. Adherence to the daily vitamin D3 administration was monitored by weighing returned bottles and parental report.

Endpoint(s)

Participants will attend three clinic visits (0, 3.5 ± 0.5 , and 7 ± 0.5 months), each coinciding with their usual medical visit. The enrolment visit (visit 1) was usually be conducted in-person, but the following visits 2 and 3 could be conducted in-person or remotely at the discretion of the physician and parents' preference in accordance to the child's health status, particularly during and after the pandemic.

Covariates

As the randomization was stratified by clinical site, the site of enrollment will be considered as a covariate in the analyses. Several baseline covariates will be considered as potential effect modifiers in subgroup analyses (e.g., BMI, atopy, serum 25OHD levels, asthma phenotype, sex, skin color, pre-emptive vs. daily ICS therapy, past morbidity, type 2 vs.non-type 2 inflammation and prescribed Step therapy using GINA 2024) and assessed at baseline. The quantity of vitamin D3 effectively administered to each participant will be ascertained after baseline covariates have been collected. Serum values for vitamin D during follow up may be considered as a marker of effective adherence in per-protocol analyses.

Adherence and protocol deviations

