Adherence to the protocol will be defined as participants having no major protocol deviations, as specified in the protocol's list of major deviations (see 'per-protocol sample'). Specifically, participants must have received at least 50% of the correct bolus dose under nursing supervision in the clinic and consistently taken the daily supplement as prescribed. In the pilot trials, adherence to the bolus dose was ensured by nursing administration in the clinic, and median adherence to daily supplement administration was over 92%, based on the weighing of returned bottles.

Major protocol deviations that will be reported and may result in changes to the analysis include instances where the wrong study drug was administered, the study bolus was not administered or less than 50% was swallowed, daily supplement bottles were not provided or collected, patients missed the daily supplement for 40 or more days, unblinding of study treatment occurred, ineligible patients were randomized, or bolus administration occurred without necessary lab results or despite abnormal results in patients with low calcium intake. Any deviation impacting patient rights, safety, welfare, or the integrity of the study data will also be considered.

Handling of missing values and other data conventions

A nested loop of imputation of missing values with regression (to adjust for baseline variables) and bootstrapping (to estimate uncertainty) will be used. This approach reduces bias, ensures imputed values reflect baseline differences, and provides robust estimates of variability and confidence intervals, thereby minimizing the impact of missing data and ensuring robust and reliable results.

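### The SAP leaves open an unspecified serum 25OHD criterion for per-protocol adherence, although treatment itself moves 25OHD and the criterion would mean something different in each arm

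*SAP*

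**What the plan says.** The Covariates section ends with the sentence "Serum values for vitamin D during follow up may be considered as a marker of effective adherence in per-protocol analyses". No threshold, measurement time or distinction between arms follows, there or elsewhere in the SAP.

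The section just before it, Exposure(s) of interest, says of the active treatment: "The intervention is designed to ensure a rapid and sustained increase in serum vitamin D levels, providing maximal group separation". Of the comparator it says: "The control group receives 2 identical placebo boluses and a daily placebo dose". It also records how daily intake was followed: "Adherence to the daily vitamin D3 administration was monitored by weighing returned bottles and parental report".

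The formal definitions do not use serum values. Analysis sets/Populations/Subgroups builds the per-protocol sample on correct study drug, no unblinding, eligibility at randomisation, absence of other serious deviations, and intake, the last as "swallowed more than 50% of Study Bolus, missed daily supplement intake for fewer than 40 days (or less than 20% of expected intake". Adherence and protocol deviations opens with "Adherence to the protocol will be defined as participants having no major protocol deviations" and refers back to that sample.

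Two further places matter. Handling of missing values and other data conventions makes the comparison of per-protocol with intention-to-treat results the plan's answer to non-compliance. Descriptive analysis of serum vitamin D already provides for summaries of 25OHD by visit and group.

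**The concern.** Follow-up 25OHD is a consequence of the allocated treatment. As a measure of whether a child took the study product it carries some information in the vitamin D arm and none in the placebo arm. A per-protocol set that depends on it no longer compares like with like. In one arm it would sort children partly by intake and partly by how their serum level stands for other reasons. In the other arm it would sort them only by those other reasons.

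The SAP itself points to such reasons. Appendix 3 treats skin colour as a stand-in for differences in vitamin D synthesis, a sun exposure questionnaire is collected, recruitment ran year-round from 2022, and the exclusion criteria bar only non-study supplements above 400 IU/day. The Introduction adds that insufficiency "is associated with more URTI and OCS use", so the marker may be related to the primary outcome as well.

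At stake is the credibility of the per-protocol sensitivity analysis. An optional criterion with no stated rule also leaves room to settle membership of that set after results by arm are known.

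**Working it through.** The SAP attaches no figure to this sentence, so there is nothing to reproduce. The check has two parts: a reading of the text, and an illustration on assumed inputs.

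**1. Reading.** Set three statements together: treatment is meant to separate the arms on serum level, controls take placebo, and serum level may mark adherence. If the first two hold, the third cannot work in the placebo arm. The per-protocol and adherence definitions contain no serum item, so the Covariates sentence opens a second, undefined route to the same set.

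**2. Share kept by a common cutoff.** Assume 25OHD is normal within each arm with equal SD, the active mean lies d SD above placebo, and the cutoff is c SD above the placebo mean. The share kept is Φ(−c) in placebo and Φ(d − c) in the active arm. Both c and d are assumptions.

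| c | Placebo kept | Active kept, d = 1 / 1.5 / 2 / 3 |
|---|---|---|
| 0.5 | 31% | 69% / 84% / 93% / 99% |
| 1.0 | 16% | 50% / 69% / 84% / 98% |

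With 323 children randomised 1:1, about 161 per arm, c = 0.5 would keep about 0.309 × 161 ≈ 50 placebo children and drop about 111, whatever their intake. With d = 2 it would keep about 0.933 × 161 ≈ 150 active children.

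**3. Filtering the active arm only, no true treatment effect.** Let S be a child's standing within the arm in SD units and let the OCS rate be proportional to exp(bS), where b = ln(rate ratio per SD). Keeping the top share k (S above q, with Φ(−q) = k) gives

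IRR = Φ(b − q) / k.

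Example: rate ratio 0.80 per SD, b = −0.2231, k = 0.25, q = 0.6745. Then Φ(−0.8976) / 0.25 = 0.1847 / 0.25 = 0.74.

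| Rate ratio per SD (assumed) | 90% kept | 75% | 50% | 25% |
|---|---|---|---|---|
| 1.00 | 1.00 | 1.00 | 1.00 | 1.00 |
| 0.95 | 0.99 | 0.98 | 0.96 | 0.94 |
| 0.90 | 0.98 | 0.95 | 0.92 | 0.87 |
| 0.80 | 0.95 | 0.90 | 0.82 | 0.74 |

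A simulation with 2,000,000 children per arm gives the same values.

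**4. A common cutoff, no true treatment effect.** With the same model,

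IRR = [Φ(d − c + b) / Φ(d − c)] ÷ [Φ(b − c) / Φ(−c)].

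Example: rate ratio 0.90 per SD, b = −0.1054, c = 0.5, d = 2. Active: 0.9184 / 0.9332 = 0.984. Placebo: 0.2725 / 0.3085 = 0.883. IRR = 0.984 / 0.883 = 1.11.

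Over c = 0.5 and 1.0 and d = 1 to 3, the IRR is 1.00 if 25OHD is unrelated to risk, 1.03 to 1.08 at 0.95 per SD, 1.07 to 1.17 at 0.90, and 1.16 to 1.41 at 0.80. The retained placebo children are those with naturally high levels, so the distortion runs against vitamin D.

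**The case against.** The sentence is permissive. It sits under Covariates rather than with the population definitions, fixes no rule, and does not say that any child leaves the per-protocol set. It could mean no more than a descriptive check on exposure, or a look for non-study vitamin D in the placebo arm. The binding definitions already rest on intake and deviations, and an optional extra marker does not strictly contradict them. The analysis affected is a sensitivity analysis.

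All of this stands, and it limits the point. A reader might infer that the SAP plans to keep only high responders in the vitamin D arm while leaving placebo untouched, and so to tilt the result towards benefit. The text does not support that. Such one-sided loss follows only if the cutoff is applied to the active arm alone, which the SAP never proposes. Even then, a lenient cutoff removes few children: with 90% kept, the null IRR stays between 0.95 and 1.00 over the assumed range. A common cutoff could push the other way.

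Nor is it right that a serum rule could not be applied blind. A common cutoff could be, although an arm-specific one would need the allocation. The view that serum response varies with baseline level or BMI should not be used as a premise either, since the SAP lists these only as hypothesised effect modifiers.

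The objection does not rescue the marker itself. Used as a description it is harmless, but the sentence calls it an adherence marker for per-protocol analyses, and in that role no rule treats both arms alike.

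**Conclusion.** The point holds in a limited form. The SAP permits, without specifying, an adherence marker that treatment drives, that cannot show intake of placebo, and that is not specific to intake in the active arm. Any per-protocol rule based on it would select on different grounds in each arm.

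Neither the size nor the direction of the bias can be derived from the document. The IRRs of 0.74 to 1.00 (active arm filtered) and 1.00 to 1.41 (common cutoff) rest on assumed normal distributions, arm shifts, cutoffs and strengths of association. The SAP says low vitamin D goes with more OCS use but gives no strength. The value of 0.74 resembles the 25% reduction the trial seeks, but it needs three quarters of the active arm to be dropped under the strongest assumed association. It should not be read as an expected result.

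The primary analysis is by intention to treat and does not change. This is a minor correction to a sensitivity analysis.

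**What to change.** Delete the Covariates sentence, or replace it with a statement that follow-up 25OHD is descriptive only and plays no part in defining adherence or per-protocol membership. Let the items already listed under Analysis sets/Populations/Subgroups and Adherence and protocol deviations alone define the set. These include bolus swallowed, daily doses missed (from bottle weights and parental report), eligibility and no unblinding, all of which can be judged the same way in both arms. Keep follow-up 25OHD in the planned summaries by visit and arm, where it shows the separation achieved.

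The cost is a change of wording. Bolus administration and bottle returns have their own case report forms, so no new data are needed. The small loss is that serum level no longer serves as an objective check on intake in the active arm.
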